The aims of the study are to (1) Determine the feasibility and acceptability of Wits Workout among 120 intervention group recipients who receive the program at 8 locations in Illinois; and (2) Use a randomized trial to examine the preliminary efficacy of Wits Workout on changes in the primary outcomes of cognitive functioning, and secondary outcomes of self-efficacy, socialization, sleep, stress and physical activity levels following the 12-week intervention (3 months) and explore maintenance effects at 6 months (3-months post-intervention) compared to a waitlist control.

Hypotheses: At three and six-month posttests, intervention participants compared to controls will differentially improve with respect to (1) PROMIS^{6,7} self-reported cognitive function measures; (2) scores on the Telephone Interview for Cognitive Screening (TICS); and (3) self-efficacy, socialization, sleep, stress and physical activity levels.

Research Design

We propose to conduct a two-arm randomized controlled trial with a treatment (workshop) group and wait-list control group. We will assess participant outcomes at baseline, immediately post-workshop (3-months) and at 6-months to assess maintenance of treatment effects.

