Qualitative Outcomes. We will conduct focus groups with participants 3 months after the conclusion of the workshops to learn more about the impact of the workshop on participant's health behaviors and their thoughts about how the program was delivered and evaluated.

[figure not shown]
Outcome Measures. We will examine the effects of participation in Wits Workout on the primary outcome of cognitive functioning and secondary outcomes of improved social satisfaction, self-efficacy, quality of life and sleep, reduced stress, and increased physical activity using the following measurements: Cognitive functioning will be assessed using the PROMIS Cognitive Function- Short Form 8a^{6,7} and the Telephone Interview for Cognitive Status (TICS). ^{8,9} TICS is a brief, standardized test of cognitive functioning designed to be measured over the telephone. Social-satisfaction will be assessed using the Cutrona Social Provisions Scale¹⁰. Self-efficacy will be assessed using the PROMIS Item Bank v1.0 - General Self-Efficacy. ⁶ Sleep will be assessed using the Pittsburg Sleep Quality Index (PSQI).¹³ Stress will be assessed using the Perceived Stress Scale.¹⁴ Physical activity will be assessed using the Physical Activity Scale for the Elderly (PASE).¹⁵

Participant inclusion/exclusion criteria: 1) age 50+; 2) English speaking /understands English; 3) No self-reported serious mental illness or diagnosis of Alzheimer's or other dementia related disease, and a score of 27 or higher on the TICS cognitive assessment during the screening call.

Procedures

Participants will be recruited through UI Extension utilizing community partners, the Extension website, Extension newsletters, and multiple media outlets, including news releases, fliers, and social media. Upon registering for the program, participants will be contacted and invited to take part in the research study. Those interested will be screened

for inclusion into the study with a brief telephone interview which includes the TICS assessment. Participants who are eligible will be sent a consent form and baseline assessment. University of Illinois at Chicago will provide institutional review board approval. All survey assessments will be administered online unless a participant is unable to complete the survey online in which case s/he will be offered the opportunity to take the survey via phone with a researcher or to receive a paper copy with a selfaddressed, stamped return envelope. Once the

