baseline assessment is completed, participants will be randomized into two groups by a member of the research team. The treatment group will receive the 12-week workshop and the waitlist control group will receive the treatment after the six-month posttest is complete (see Figure 1). The first posttest and TICS will be administered by a member of the research team to both the workshop and control groups immediately following the end of the 12-week program (3 months). The 6-month follow-up assessment and TICS will be administered 3 months after the end of the program to both the workshop and control groups by a member of the research team. Reminders to complete the survey will be sent by a research team member by email and/or phone. Participants will be provided a \$20 gift card upon completion of each survey that will be administered by a research assistant. A "reunion" event will take place three months after the last *Wits Workout* session for the workshop group only. The reunion will give participants an opportunity to reconnect informally and it will enable the research team to conduct the follow-up focus groups. Qualitative methods are particularly well suited for the assessment of simulated changes in behavior and will provide us richer detail than the surveys alone¹⁶.

Power Analysis and Sample Size Estimation. In the cognition literature, a 1-3 point decrease in the Mini Mental State Exam score has been shown to be indicative of a meaningful decline. Our primary outcome, cognitive functioning, will be assessed using the TICS -- a telephone version of Mini Mental State Exam which is administered in person. Both measures correlate highly.^{9,10} Among older adults with normal cognition, which is our target sample for this trial, an effect size of 0.29 was considered clinically meaningful.¹¹ With this more conservative effect size of .20, an alpha of .05/6 = 0.008 9adjusted for multiple outcome measures and comparisons across rural and urban samples), for 3 time points (0-12-24 weeks), power set to .80, and an estimated correlation of .50 among measures, we need a total of 208 participants. Accounting for ~15% attrition, we will target to recruit a total of 240 participants for this trial. **Data Analysis**

Quantitative data. We will conduct 3x2 repeated measures ANOVAs to examine time (pre vs. post vs. follow-up),

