group (intervention vs. waitlist control), and interaction effects. The quantitative measures that will be evaluated using this statistical model include measures of social satisfaction and support, perceived well-being and quality of life, physical activity and exercise, self-efficacy, and the cognitive functioning scores. Covariates such as demographics [age, biological sex, geographic location (rural vs. urban)], and attendance to the Wits Workout program will be accounted for in the analyses. As a secondary analysis, we will also examine correlations between the demographic characteristics and the study outcomes. Drs. [name] and [name] have experience in analyzing similar large datasets from randomized controlled trials using these analysis strategies.

Qualitative data. [name] will conduct the focus groups using a guide to facilitate the discussion. The guide will include nine questions that will provide more in-depth detail about outcomes experienced by the participants (i.e. *In what ways did participating in Wits Workout impact your health behaviors?*) as well as questions that will provide details about their perception of the program (i.e. *What suggestions do you have to improve the program?*). We will audiotape and transcribe the focus groups. Three research team members will review all transcripts to develop an initial code book. We will then apply the codebook to a subsample of the transcripts individually then meet to discuss any areas where we are not coding consistently and adjust the codebook accordingly. We will then apply the same technique to another subsample of transcripts. Once we are certain that coding is consistent and the codebook is finalized, [name] will code the transcripts using NVivo QSR qualitative software. She will use an inductive thematic analysis process to analyze the data. Themes will be discussed and finalized with the research team.

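### The 3x2 repeated-measures ANOVA names no primary term or visit contrast and does not adjust for the pre-randomisation baseline; 208 fits only a group main effect with about 38% power if the arms start equal

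*Combined protocol and SAP*

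**What the plan says.** Under Data Analysis, Quantitative data: "We will conduct 3x2 repeated measures ANOVAs to examine time (pre vs. post vs. follow-up", and then "group (intervention vs. waitlist control), and interaction effects". No term is called primary and no contrast at a given visit is written. The adjustment set is "Covariates such as demographics [age, biological sex, geographic location (rural vs. urban)], and attendance to the Wits Workout program". The list is open-ended, but it does not name the baseline score of the outcome.

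The target is clearer earlier in the document. Overall Aims looks for change "following the 12-week intervention (3 months) and explore maintenance effects at 6 months (3-months post-intervention) compared to a waitlist control", and the Hypotheses say "At three and six-month posttests, intervention participants compared to controls will differentially improve with respect to" the listed measures. Under Procedures, the order of events is that once the "baseline assessment is completed, participants will be randomized into two groups by a member of the research team".

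The Power Analysis section states "Our primary outcome, cognitive functioning, will be assessed using the TICS". It takes an effect size of .20 (metric not given), alpha .05/6 = 0.008, three time points, correlation .50 and 80% power. It arrives at 208 participants, and recruits 240 to allow for about 15% attrition.

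**The concern.** The three ANOVA terms answer different questions. The time effect says nothing about the intervention. The group main effect averages in the baseline visit, where randomisation rules out a treatment effect. The interaction does address differential change, but its two degrees of freedom do not say at which visit the arms differ, so by itself it cannot show maintenance. With none of these named as primary, the result to be reported can be chosen after the data are seen.

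Baseline is collected before allocation, so the arms are equal there in expectation. An analysis that uses this gains precision at no cost in data. Treating baseline as one more outcome gives that precision up.

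Two features move the plan away from the plain interaction test. Attendance is measured after randomisation and is nil by design in waitlist controls until after 6 months. The 8 workshop groups described under Intervention do not appear in the model.

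**Working it through.** **Inputs from the document.** Alpha .05/6 = .00833 (printed 0.008); correlation ρ = .50; m = 3 visits; 240 recruited, 1:1, 15% attrition, so 240 × .85 / 2 = 102 completers per arm.

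**Assumptions.** The .20 is Cohen's f, so the difference is 2 × .20 = 0.40 SD; two-sided tests; equal variance at all visits; no attendance covariate; no clustering unless stated.

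**1. The plan's own figure.** For the group main effect, λ = N f² m / [1 + (m−1)ρ] = 208 × .04 × 3 / 2 = 12.48. With 1 and 206 df and alpha .008, power is .802, so 208 reproduces. Other readings at alpha .008 do not: interaction at f = .20 needs 64, main effect at f = .10 needs 818, interaction at f = .10 needs 244.

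**2. The same term with equal baselines.** With differences 0/.40/.40 at baseline, 3 and 6 months, the mean difference is .80/3 = .267. The variance of a participant's mean is (1 + 2ρ)/3 = .667. Then λ = (208/4) × .267² / .667 = 5.55, and power is .381 at alpha .05/6.

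**3. Planned interaction.** λ = (n/2) Σ(d_t − d̄)² / (1−ρ), with 2 and 404 df.
- 0/.40/.40: 51 × .1067 / .5 = 10.88, power .635.
- 0/.40/0: the sum of squares is again .1067, so power is the same .635. A lasting and a vanished effect are equally detectable.

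**4. Joint baseline-adjusted test.** λ = (n/2) d′V⁻¹d, where V has diagonal 1−ρ² = .75 and off-diagonal ρ−ρ² = .25, with 2 and 200 df.
- .40/.40: 51 × .32 = 16.32, power .851.
- .40/0: 51 × .24 = 12.24, power .698.

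**5. One visit, 0.40 SD.**
- Change from baseline: variance 2(1−ρ) = 1.00, SE = √(2/102) = .140, noncentrality 2.86, power .577.
- Baseline-adjusted: variance .75, SE = .866 × .140 = .121, noncentrality 3.30, power .736.

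**6. How far the one-visit gain depends on the assumptions.**

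| Case | Change | Adjusted |
|---|---|---|
| 0.40 SD, ρ = .30 | 40% | 63% |
| 0.40 SD, ρ = .50 | 58% | 74% |
| 0.40 SD, ρ = .70 | 85% | 91% |
| 0.40 SD, ρ = .80 | 97% | 98% |
| 0.58 SD (0.29 read as f), ρ = .50 | 93% | 98% |
| 0.29 SD, ρ = .50 | 28% | 39% |
| 0.20 SD, ρ = .50 | 11% | 16% |

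Eligibility requires a TICS score of at least 27 at screening, which may narrow the baseline. If baseline variance were halved (assumed) with slope .5 and residual variance .75 unchanged, the change variance would be .25 × .5 + .75 = .875. The comparison becomes 65% against 74%.

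**7. Clustering.** There are 102/8 = 12.75 completers per workshop, so the workshop-arm variance is multiplied by 1 + 11.75 × ICC. A Satterthwaite approximation with 7 df for that arm takes the 74% to about 63% at ICC .01 and 49% at ICC .05 (both assumed).

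**8. Attendance and ignored clustering.** A simulation of 6,000 runs assumed attendance of 0 in controls, a mean of about 9 of 12 in the workshop arm, and correlation 0.3 with a participant's stable level. Adding attendance raised the SE of the group term from .14 to .41 in the change model, and power fell to about 5%. In the baseline-adjusted model the group estimate was biased by about −0.41 SD, and type I error was 6.7% against a nominal 0.83%. Without attendance, ignoring an ICC of .02 to .05 gave type I error of about 1.1% to 2.4%.

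**9. Late-building effect, 0/.20/.40.** Adjusted 3-month contrast: .20/.121 = 1.65, power 16%. Interaction: λ = 51 × .08 / .5 = 8.16, power 47%.

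**The case against.** The sponsor can fairly say that the Hypotheses already identify differential improvement at both visits, that Overall Aims ranks 6 months as exploratory, and that visit contrasts can be drawn from the same ANOVA. Aim 2 is also described as preliminary efficacy. This stands: the target can be inferred. What is missing is the step from that target to a named test, and the sample-size paragraph uses a different term.

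A reader might infer that the ANOVA is an invalid test of the hypothesis. The documents do not support that of the plain interaction, which validly tests differential change with complete data and independent participants. Nor do they support the opposite inference, that only precision is lost. The plan adjusts for attendance and leaves out workshop groups, so it is not the plain interaction.

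A reader might also take 58% to 74% as the gain over the planned test. The 58% belongs to a one-visit change contrast that the plan does not name. The like-for-like comparison is interaction against joint adjusted test, where the gain depends on the pattern of effect. The effect-size metric is uncertain too. The plan calls .20 more conservative than 0.29; if both are f, 0.29 is 0.58 SD, where adjustment adds little.

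Finally, a reader might infer that incomplete records will be deleted. That is a common software default, but the plan does not say it.

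**Conclusion.** The point holds on two counts. First, the analysis does not carry the hypotheses into a primary term or visit contrasts, and it leaves a baseline collected before randomisation unused for adjustment. On the stated assumptions, like-for-like power is 63% against 85% for a sustained effect and 63% against 70% for one gone by 6 months. The one-visit contrast has 58% against 74%, and that gain nearly disappears at 0.58 SD or at correlation .80. Second, 208 belongs, of the readings checked, to a main effect that requires the arms to differ at baseline. Without that difference its power is about 38%.

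The adjusted figures hold only with attendance removed. With an assumed ICC of .01 to .05 and small-sample degrees of freedom, the 74% is about 63% to 49%. The 0.40 SD is an inference from the exact reproduction of 208, not a figure in the document. These results call for a corrected power statement; they do not establish that enrolment must rise.

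**What to change.** 1. Analyse the 3- and 6-month scores in a linear mixed model using all available scores from everyone randomised. Include baseline score, age, sex, rural/urban, group, visit and group-by-visit. Use an unstructured within-person covariance and a workshop random effect in the intervention arm, with small-sample degrees of freedom. Leave attendance out of this model. For TICS, say which pre-randomisation score serves as baseline, since the only one explicitly described is from the screening call.
2. Following aim 2, name the 3-month between-arm difference as the primary contrast and the 6-month difference as the maintenance contrast.
3. Restate the power for the 3-month contrast in place of the group main effect, giving the effect-size metric and the assumed correlation and ICC. Leave enrolment unchanged.

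The cost is a rewritten analysis paragraph and power paragraph, with matching code and no new data collection. There are two real downsides. On these assumptions the stated power would fall below 80%. If the effect builds late, a 3-month primary contrast does worse than the interaction (16% against 47% for 0/.20/.40 SD).

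### The three-visit repeated measures ANOVA, in its standard form, discards collected 3-month results of anyone who misses the 6-month visit; this costs precision and can bias the 3-month contrast if late loss depends on the score differently by arm

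*Combined protocol and SAP*

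**What the plan says.** Data Analysis, Quantitative data, names one model for all quantitative outcomes: "We will conduct 3x2 repeated measures ANOVAs to examine time (pre vs. post vs. follow-up", followed by "group (intervention vs. waitlist control), and interaction effects". No other efficacy model appears.

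The Hypotheses under Overall Aims need a result at each later visit: "At three and six-month posttests, intervention participants compared to controls will differentially improve with respect to" the listed outcomes. The second aim, in the same section, gives the later visit a softer role, to "explore maintenance effects at 6 months (3-months post-intervention) compared to a waitlist control".

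The 3-month outcome is collected in both arms before the 6-month visit is due. Procedures says "The first posttest and TICS will be administered by a member of the research team to both the workshop and control groups" straight after the 12 weeks, and "The 6-month follow-up assessment and TICS will be administered 3 months after the end of the program to both the workshop and control groups". Randomisation follows completion of the baseline assessment, so baseline should be present for everyone randomised.

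Power Analysis and Sample Size Estimation says "we need a total of 208 participants" and then "Accounting for ~15% attrition, we will target to recruit a total of 240 participants for this trial". The 15% is not divided between losses before and after month 3. The only other text on attrition, under Intervention, says it will be documented from workshop attendance. That covers neither the control arm nor missed assessments.

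The document gives no analysis set, intention-to-treat rule, imputation or mixed model, missing-data assumption or sensitivity analysis.

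**The concern.** A standard three-level within-subject ANOVA needs a value at baseline, 3 months and 6 months for each person. Someone who completes baseline and the 3-month posttest and then misses 6 months leaves the whole analysis, including any 3-month comparison. Someone who misses 3 months but returns at 6 months likewise loses the 6-month result.

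Two things are at stake. The first is precision: results already collected go unused. The second is validity: the 3-month contrast is restricted to people selected by a later event. If that selection works differently in the two arms, the comparison no longer has the full protection of randomisation.

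The design gives the arms different reasons to stay. By month 3 the workshop arm has had the programme and has a reunion ahead at about the 6-month point. The control arm is still waiting for a workshop that comes only after the 6-month assessment.

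**Working it through.** **Inputs from the plan.** 240 randomised, 120 per arm; three visits; correlation .50 among measures; alpha .05/6 = 0.00833, written as 0.008; effect size .20 with no metric stated; power .80; attrition about 15%.

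**The plan's own figure.** Reading .20 as Cohen's f, and taking the between-group main effect of a repeated measures ANOVA with m = 3 complete visits:

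λ = f² · N · m / (1 + (m − 1)ρ) = 0.04 × 208 × 3 / (1 + 2 × 0.5) = 24.96 / 2 = 12.48

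With 1 and 206 degrees of freedom and alpha .008, power is 0.802, so 208 is reproduced. Then 208 × 1.15 = 239.2, rounded to 240. Computing 208 for complete data and adding a margin for losses fits an analysis of people with all three visits, although the document does not say so.

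**How many results could go.** 0.15 × 240 = 36 people lost, leaving 204 with all three visits. If every loss falls after month 3, all 36 have a 3-month result that the standard ANOVA would not use. If half do, the number is 18.

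**Precision.** Take each measure's SD as 1. The change from baseline to 3 months has variance 2(1 − 0.50) = 1. The standard error of the between-arm difference in change is:

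- everyone with baseline and 3 months (120 per arm): √(2/120) = 0.129
- completers, all 15% lost late (102 per arm): √(2/102) = 0.140

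**Bias, by simulation.** Assumptions that are not in the plan: no true effect; normal scores; late loss random in controls; in the workshop arm, late loss more likely with a low 3-month score, with a logistic slope per SD as shown; the same overall late-loss rate in both arms. The test is on change from baseline to 3 months among completers. The half-late rows model the 7.5% lost late and no earlier loss.

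| Lost after month 3 | Slope | Bias (SD) | Rejection at .05/6 (nominal 0.83%) |
|---|---|---|---|
| 15% (all late) | 0.5 | about +0.034 | about 1% |
| 15% (all late) | 1.0 | about +0.066 | about 1.5% |
| 15% (all late) | 1.5 | about +0.087 | about 2.4% |
| 7.5% (half late) | 0.5 | about +0.017 | about 1% |
| 7.5% (half late) | 1.0 | about +0.031 | about 1% |
| 7.5% (half late) | 1.5 | about +0.045 | about 1% |

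Using all collected 3-month results gives a bias of about 0.00 SD and rejection of about 0.9% in these settings. That is what a likelihood model with visit as a category uses for this contrast.

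**Other patterns, all 15% late.**

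- Same dependence in both arms, no true effect: bias about 0 and rejection about 0.8%.
- Same dependence in both arms, true effect 0.20 SD: bias of −0.003 SD (slope 0.5) to −0.02 SD (slope 2), towards zero.
- Opposite dependence in the two arms, slope 1, no true effect: about +0.13 SD and rejection about 4.6%. This is an extreme case.

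**The case against.** Several points on the other side stand.

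- **The plan never says completers only.** A reader might infer that it prescribes deletion. It does not. Deletion is the default behaviour of the named method, and no text overrides it.
- **Dependence on the score is not enough.** A reader might conclude that the 3-month estimate is biased whenever withdrawal depends on the 3-month result. With the same dependence in both arms there is no bias under no true effect, and only a small bias towards zero otherwise.
- **Placing all 15% after month 3 is an upper case.** The plan does not split attrition, and its other mention of it concerns the 12 workshop weeks. A person lost before the 3-month posttest has no 3-month result to discard.
- **The 6-month visit is not clearly secondary.** The aim speaks of exploring it, but the Hypotheses name both visits. It cannot be said that a merely exploratory visit filters the important one.
- **The bias should not be set against 0.29.** That figure and .20 have no stated metric, and 208 is reproduced with .20 as Cohen's f, so a comparison in SD units is unsupported.
- **Retention is planned for.** There are phone and paper options, reminders, a $20 card per survey and the reunion. After month 3 nobody is leaving a workshop; only assessments remain.
- **The 3-month contrast is not itself specified.** Data Analysis names only time, group and interaction effects. The contrast is, however, what the Hypotheses require.

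These points reduce the size of the problem. None supplies a rule that keeps partial data.

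**Conclusion.** The point holds in a limited form. Followed as written, with the ANOVA in its standard form, the plan would discard 3-month results collected from people who miss only the 6-month visit. The loss of precision is modest and needs no assumption about why people leave, only that some leave late. Bias needs more: late withdrawal that depends on the 3-month score differently in the two arms. The design makes this plausible, but the document gives no evidence for it.

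Under the assumed workshop-arm-only patterns, the bias at the 3-month contrast is below 0.1 SD even in the all-late case. Inflation of the error rate at the plan's alpha is noticeable only there, and with half the loss late it is close to nominal. These sizes rest on the assumed slopes, timing and normal scores; only the sample size, correlation, alpha and attrition rate are the plan's. A change is worth making because it is cheap and uses data the trial will already hold, not because serious bias has been shown.

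**What to change.** In Data Analysis, state that all randomised participants are analysed by assigned arm, with every observed visit included, in a likelihood-based repeated-measures model. Its terms would be group, visit as a category, group-by-visit, and the demographic covariates already listed (age, sex, rural or urban location). Report group contrasts at 3 and at 6 months. Keep the completers-only 3x2 ANOVA as a sensitivity analysis, and tabulate missing visits by arm.

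The cost is a few lines of text, with no new data or visits. The small downside is reliance on a missing-at-random assumption, which should be stated; it is weaker than what the completers-only analysis needs. Settling this before the data are seen also removes a later choice between completers and all observed data.

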Intervention. Wits Workout will take place over 12 weeks, one hour per week. The training will be delivered by 5 UI Extension faculty educators who were trained by the Extension faculty educators who developed the program. Each week includes a themed module with four activities and a training component featuring educational topics such as a) exercising regularly; c) engaging the brain with new and intellectually stimulating challenges; d) participating in social activities; e) getting enough sleep; and f) reducing stress. The workshop will be offered in-person in 8 areas with a target of 20 attendees per urban workshop and 12 attendees per rural workshop for a total of 120 workshop participants. The waitlist control participants (n=120) will be offered the workshop after the 6-month study period is completed. All COVID safety requirements will be in place at the workshop sites. A fidelity assessment tool will be developed by the research team and implemented at all program sites. All Wits Workout leaders will be observed teaching two sessions of the program by one of the study investigators. After the first observation occurs, the fidelity evaluator will debrief with the leader and the evaluator will follow up with a written evaluation that includes strengths, areas of improvement (including ways in which they adhered and/or strayed from the program content and facilitation techniques outlined in the Wits Workout Leader's Guide), and suggestions for increasing fidelity in their teaching. A second observation will occur within the several weeks of the first observation with the goal of continuous process improvement from the first

to the second evaluation. UI faculty educators leading the workshops will record attendance over the 12 weeks and report to the investigative team. Attrition as well as completion rates will be documented based on workshop attendance.

Sample. We will offer Wits Workout to a minimum of 240 older adults (120 treatment and 120 delayed treatment controls) in three urban and five rural areas of Illinois (see

Location	Urban/Rural	Numbers	Waitlist
Chicago Area	Urban	20	20
Chicago Area	Urban	20	20
Champaign	Urban	20	20
St. Joe/Paxton	Rural	12	12
Sterling	Rural	12	12
Mattoon	Rural	12	12
Macomb	Rural	12	12
Marion	Rural	12	12
Total Participants		120	120

Table 1).

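### Workshop attendance, which arises after randomisation and only in one arm, is listed as a covariate in the between-group models

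*Combined protocol and SAP*

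**What the plan says.** Data Analysis, Quantitative data, names a single between-group model: "We will conduct 3x2 repeated measures ANOVAs to examine time (pre vs. post vs. follow-up"), "group (intervention vs. waitlist control), and interaction effects". The covariate sentence that follows lists age, biological sex and rural or urban location, and adds that "attendance to the Wits Workout program will be accounted for in the analyses". It does not say how attendance is coded, whether it is crossed with time, or that any model is fitted without it. The only analysis labelled secondary is a different one: "As a secondary analysis, we will also examine correlations between the demographic characteristics and the study outcomes".

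Other sections fix what kind of variable attendance is. Under Procedures, randomisation follows the baseline assessment, and "the waitlist control group will receive the treatment after the six-month posttest is complete". Under Intervention, "UI faculty educators leading the workshops will record attendance over the 12 weeks and report to the investigative team". The Hypotheses paragraph states the question as one between arms: "intervention participants compared to controls will differentially improve with respect to" the listed outcomes.

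**The concern.** Age, sex and location are fixed before randomisation, so adjusting for them leaves the comparison of the arms intact. Attendance is a consequence of allocation and is itself a measure of treatment received. It is zero by design in every control throughout follow-up.

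Adjusting for it has two effects. It removes from the group effect whatever benefit is delivered through the sessions. It also brings in the difference between people who attend well and people who do not, which randomisation does not balance. A useful program can then appear inert, and an inert one can appear harmful. Because this is the only between-group model, the primary cognitive outcome is affected along with the rest.

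**Working it through.** **Inputs from the documents.** Two arms at 1:1; three assessments; correlation .50; effect size .20; alpha .05/6, written as 0.008; power .80; 208 analysed (104 per arm); 12 weekly sessions.

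**Assumptions.** Attendance in the workshop arm has mean 9 and SD 3 sessions, with 6/4 and 10/2 as the range. Outcomes have unit variance and equal correlations, data are complete, and baseline covariates are omitted as unrelated to arm. Unless noted, alpha is .05/6, attendance is entered as raw sessions, and controls are 0.

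**1. Reproducing 208.** The metric of .20 is not stated; read as Cohen's f, it reproduces the figure. For the group effect, noncentrality = f²·N·m / (1 + (m−1)ρ) = 0.04 × 208 × 3 / 2 = 12.48 on 1 and 206 df. Power is 80.2% at alpha .008 and 80.6% at .05/6. For group-by-time, f²·N·m / (1−ρ) = 0.04 × 208 × 3 / 0.5 = 49.9, with power above 99%; that test would need only 64 participants. So 208 matches the group main effect.

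**2. What the adjusted coefficient estimates.** With every control at 0, the attendance slope γ (outcome per session) is estimated in the workshop arm alone. The group coefficient is the workshop-arm line read at zero sessions, minus the control mean: (difference between arms) − γ × (mean sessions).

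**3. Loss of precision.** The squared correlation of group with attendance is mean² / (mean² + 2·SD²) = 81/99. The variance inflation factor is therefore 1 + mean²/(2·SD²).

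| Mean / SD | Inflation | Noncentrality | Power, group effect |
|---|---|---|---|
| no attendance term | 1 | 12.48 | 81% |
| 6 / 4 | 2.1 | 5.87 | 41% |
| 9 / 3 | 5.5 | 2.27 | 13% |
| 10 / 2 | 13.5 | 0.92 | 5% |

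This is loss of precision alone: the effect is taken as unrelated to sessions, so there is no bias. As the formula requires, it is 0.40 SD (2f) at every visit.

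**4. Effect of 0.40 SD at 3 and 6 months only (mean 9, SD 3).** The group effect averaged over visits is 0.80/3 = 0.27. Its standard error is √((2/3)(2/104)) = 0.113 without attendance, giving 38% power, and 0.113 × √5.5 = 0.266 with it.

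| Effect and sessions | Group estimate with attendance | Power |
|---|---|---|
| unrelated | 0.27 | 5% |
| half proportional | 0.27 − 0.13 = 0.13 (unrounded) | 2% |
| fully proportional | 0.27 − 0.27 = 0.00 | 1% |

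For group-by-time, noncentrality = 52 × (0.267² + 2 × 0.133²)/0.5 = 11.09, with power 65%. If attendance-by-time is fitted and the effect is unrelated to sessions, this becomes 11.09/5.5 = 2.02, with power about 7%. Power is about 2% if the effect is half proportional and 1% if fully proportional. If attendance enters only as a main effect, it cancels from the within-person contrasts and group-by-time is unchanged.

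**5. Program with no effect.** Suppose the outcome rises 0.3 SD per SD of attendance. At mean 9, SD 3, the group coefficient is biased by −(0.3/3) × 9 = −0.90 SD. The nominal rejection rate is 0.8%.
- Link present at every visit: the group effect is falsely rejected in 76% of trials (53% at 6/4; 80% at 10/2), and group-by-time is unbiased.
- Link present after baseline only, with attendance-by-time fitted: group-by-time is falsely rejected in 59% by simulation (37%; 65%).
- Weaker link, mean 9, SD 3: at 0.15 the two rates are about 16% and 10%; at 0.1, about 7% and 4%.

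**6. Coding.** Grand-mean centring gives the same group result as raw sessions. Centring within the workshop arm restores it: in the scenario of step 4, power is about 38% for group and 65% for group-by-time, and null rejection is about 1%. Leaving attendance missing in controls would drop the control arm under listwise deletion.

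**The case against.** The strongest reply is that the hypothesis of differential improvement is carried by group-by-time, and the plan never states an attendance-by-time term. With a main effect only and complete data, that test is untouched. This is correct. But the plan also lists the group effect as a tested term, and the stated sample size matches that term.

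Second, the fall from 80% to 13% supposes a difference at every visit, baseline included, which randomisation rules out in expectation. That also stands: 13% describes the plan's own sizing formula. With the effect confined to follow-up, the group test starts at 38%, and the loss due to attendance is from 38% to 5% or less.

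Third, the slope of 0.3 is not a document figure. At 0.1 the false rejection rate is only about 4% to 7%. That is still five or more times the nominal 0.8%, so the slope governs the size of the problem and not its existence.

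Fourth, the coding is unstated and one coding does no harm. True, but the text treats attendance like the baseline covariates, and nothing in it points to within-arm centring. Nor does describing the trial as preliminary make a post-randomisation covariate suitable for a comparison of arms. The Intervention section's separate use of attendance, for attrition and completion rates, does not confine it to that use.

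**Conclusion.** The plan is wrong as written. It places a post-randomisation measure of treatment received among the covariates of its only between-group model, and no text confines that measure to a separate analysis. With sessions attended and controls at zero, the group effect no longer estimates the effect of being randomised to the program.

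The direction follows from the design. The size rests on the assumed attendance distribution, on how far the benefit depends on sessions, and on how strongly attendance tracks the outcome; the documents give none of these. Harm to the group effect requires raw or grand-mean-centred coding. Harm to group-by-time requires attendance-by-time as well. The plan settles neither choice, so a decision that determines the result would be left until the data are available. This must be corrected before analysis.

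**What to change.** In Data Analysis, Quantitative data, delete attendance from the covariates of the between-group models. Keep age, biological sex and rural or urban location, and state that participants are compared as randomised. Add one sentence: attendance will be related to outcomes only within the workshop arm, in a separate dose-response description labelled non-randomised.

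Centring within the workshop arm would also protect the tests, but deletion is simpler and leaves nothing to coding. The cost is one phrase removed and a sentence or two added. Attendance is still recorded for feasibility; the 3x2 model, the data collected and the sample size do not change.
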